3.3 Secondary Study Endpoints

School absence and academic performance data will be provided by the NYC Department of Education.

Medicaid claims, encounter, and eligibility data for elementary students in New York City enrolled in Medicaid will be provided by New York University's Wagner School of Public Service and New York University's School of Medicine.

3.4 Primary Safety Endpoints

The care provided is usual and customary care, not high-risk. The only risk about which we are aware is a toothache. Our history suggests that this occurs in approximately 1 in 2000 children. In our experience, this occurrence is far less than the percentage of children with tooth aches prior to initiation of prevention (approximately 5 in 100 children).

4 Participant Selection, Enrollment, and Withdrawal

4.1 Study Population

The study population will be children with informed consent who do not have an allergy to silver and are attending New York City elementary schools. 76 elementary schools will be selected to participate in the study. 60 of the participating schools will have at least 50% of the student population being of Hispanic/Latino origin and 80% from low socio-economic backgrounds. Beyond these inclusion criteria, any child in the school of any race/ethnicity or socio-economic group is eligible for participation. 16 of the 76 schools have no inclusion criteria but will be purposefully selected to represent a majority of students from every major racial/ethnic and socioeconomic group. School participation will be finalized with individual principals and we will execute a memorandum of understanding (MOU) with each participating school and each community-based organization.

4.2 Participant Recruitment, Screening and Enrollment

4.2.1 Recruitment

Recruitment will be done during Caried*Away* community engagement events and in concert with all other yearly school notifications and requests for consent via informational packets sent home with the children to their parents/guardians, mailed to the parents or sent electronically by the school's system of choice. Recruitment information will contain care details written in English and Spanish, a pre-populated personalized principal recruitment letter, the parent/guardian alternate location recruitment letter, the parent/guardian recruitment flyer, a health history, the NYU Langone Health COVID-19 research participation information sheet and a blank paper informed consent form. Parents will be asked to review the forms and contact the principal investigator if they have any questions prior to signing and returning the forms to the child's school.

Paper pre-populated personalized principal recruitment letter and blank informed consent will also be distributed and written in Arabic, Bengali Bangla, Chinese, French, Haitian Creole, Korean, Russian or Urdu.

Electronic informed consent forms will also be distributed to parents/guardians of new students who have not previously consented. The Caried*Away* parent/guardian communication toolkit emails contain hyperlinks to the NYU Caried*Away* Websites and REDCap eICF's in English and Spanish and will be provided to school administrators to distribute to parents and guardians of children enrolled in the school via whichever existing method the school uses for mobile phone contact, email or electronic communication systems.

The parent/guardian recruitment flyer (English and Spanish) will also be placed Independently during Caried*Away* community engagement events as an FAQ, as a flyer for posting on school bulletin board, as an attachment included in orientation documents for dental champions (school administrative staff, ie. (Parent coordinators) and dispersed to parent/guardian via whichever existing method the school uses for mobile phone contact, email or electronic communication systems, at the discretion of the school staff.

The English and Spanish parental/guardian recruitment flyers have the following Quick Response Code (QR code) in each flyer:

English QR code:

Spanish QR code:

The QR code allows the parent/guardian to use their smart phone to take a picture of the English or Spanish QR code. Once they have taken the picture they will be asked if they wish to Open "nyumc.org" in Safari. If they choose "open" they are sent directly to the IRB approved REDCap eICF in the English or Spanish. They can then securely fill out, sign and date the eICF.

All parents/guardians of new or previously consented students will be contacted via telephone by one of our clinical team members prior to scheduling any appointments. Parents/guardians of previously consented students will be reminded that they signed a 5 year informed consent. The clinical team member will use the research participant telephone recruitment script for COVID-19 updates. They will ask the parent/guardian a few questions to assess whether it makes sense, from a safety perspective due to the COVID-19 pandemic if they wish to have their child to participate or continue to participate in this research study. After a clinical team member speaks with the parent/guardian of a new participant, the clinical team member will send the parent/guardian the Caried*Away* new enrollee email written in English or Spanish. The email will also contain a link to the REDCap eICF and provide contact information if the parent/guardian has further questions.

4.2.2 School Randomization

Beginning in the first year of the study, a total of 30 schools will be randomized (15 schools receiving simple prevention and 15 receiving complex prevention) to receive prevention twice per year. Consenting children will be followed over five years. In Year 2, 30 additional schools will be randomized to receive either simple or complex prevention twice per year. Consenting children will be followed over four years. Also in Year 2, an additional 16 schools will be selected to receive simple prevention once per year, and consenting children will be followed over four years.

4.2.3 School Rosters and Informed Consent Preparation

In August we will request that the NYC Department of Education provide an electronic roster for each school. The rosters are used to create the IRB-approved pre-populated personalized principal recruitment letter from the principal to include school name, school address, and principal/assistant principal name and date explaining the program. The pre-populated personalized principal recruitment letters, the parent/guardian alternate location recruitment letter, the parent/guardian recruitment flyer, a health history, the NYU Langone Health COVID-19 research participant information sheet and a blank paper informed consent are printed at NYUCD and distributed to each teacher or school. These packets are either sent home with the children or mailed to the parent/guardian by the school administrator.

The REDCap electronic informed consent forms are updated by the study administrator annually and each time a new modification of the consent form has been approved by the NYU Langone IRB.

4.2.4 Informed Consent

Blank IRB-approved paper informed consent will be distributed during Caried*Away* community engagement events and to students at the beginning of each school year in concert with all other school notifications. Parents can also choose to sign their child up for the program at their child's school. The blank paper informed consent will include a pre-populated personalized principal recruitment letter from the principal, the parent/guardian alternate location recruitment letter, the parent/guardian recruitment flyer, program information, a health history, the NYU Langone Health COVID-19 research participant information sheet, and the blank informed consent to be filled out for signature by the parent/guardian.

Completed parent/guardian signed and dated paper informed consent will be returned to the school and collected by the research team. This protocol aligns with other school vision, hearing, and vaccination programs. Care will be provided to all children with informed consent.

Electronic informed consent forms will be distributed in addition to the established protocol for the distribution of paper consent forms to participating sites (schools). The following protocol will be followed for eICF distribution:

Electronic informed consent can be distributed by a clinical team member using the Caried*Away* new enrollee email written in English or Spanish using the following hyperlinks:

- English language eICF: https://is.gd/CariedAwayNYC
- Spanish language eICF: https://is.gd/CariedAwayNYC_SP

Electronic informed consent can be distributed by the schools in English or Spanish using whichever existing method the school uses for mobile phone contact, in emails, or on the school's social media page in the following ways:

- NYU Caried*Away* Website URL by selecting "registering your child" 1) English
 - https://dental.nyu.edu/faculty/epidemiology-health-promotion/pcori-grant.html
 - Short URL: https://dental.nyu.edu/pcori
 - 2) Spanish
 - https://dental.nyu.edu/faculty/epidemiology-health-promotion/pcori-beca.html
- 2. Hyperlinks in English and Spanish
 - English language eICF: https://is.gd/CariedAwayNYC
 - Spanish language eICF: https://is.gd/CariedAwayNYC_SP
- 3. CariedAway email toolkit in English and Spanish

The parent or legal guardian fills out the eICF and uses 'scratch' method (mouse, stylus, or finger) to sign and then returns the completed ICF via Redcap.

The study administrator will then cross-reference the OSIS number in the original .csv file which was provided to us at the beginning of each school year by the NYC Department of Education, and verify that the correct OSIS number was provided correctly by the consenter.

The study administrator then uploads all of the informed consent PDF's to NESS via the secure and password protected ShareFile link listed below:

https://nedental.sharefile.com

NESS then uploads each student's eICF to their electronic dental record in the iPad

To facilitate accurate informed consent and student tracking we will request student rosters from the NY City Department of Education (NYC DOE). This will facilitate tracking students longitudinally. All forms will be translated into the major languages of NYC school children's parents. Those languages are Arabic, Bengali Bangla, Chinese, English, French, Haitian Creole, Korean, Russian, Spanish and Urdu.

The consent form is valid for 5 years or as long as the child is in NYC schools. If guardianship of the child changes a new informed consent will need to be signed.

4.3 Early Withdrawal of Participants

A parent may withdraw their child at any time for any reason, with either a written request or a phone call (with verification) to the PI, CRA, or school. Upon withdrawal the center is notified, and the record flagged to remove the child from the informed consent list in the data base, in the Apple iPad electronic record. Students who withdraw are not replaced.

4.4 Dental provider referral

Parents of children without a dentist or children that require an urgent referral will be provided information on local dental providers in the following ways:

4.4.1 Children without a Dentist

Parents/guardians of children without a dentist can access the Caried*Away* Website Dentist finder map. They are instructed to click on the map, type in their address and then click on the blue pins to access the name, address and phone number for that provider. All providers listed accept new patients, see children and, accept Medicaid and CHIP. Parents will also be provided with the NYU CariedAway- addition to Website Dentist Provider Map Instructions.

4.4.2 Children that require an urgent referral

Parents/guardians of children that require an urgent referral will receive the NYU Caried*Away* parent communication urgent referral email sent to them by the Caried*Away* clinical mangers. This email provides them with the CariedAway-addition to Website Dentist Provider Map Instructions. The email also provides information for the NYU Department of Pediatric Dentistry.

5 Study Device

5.1 Description

We use three agents, all are off-label. None are investigational new drugs.: fluoride varnish (2 agents), and silver-diamine-fluoride. These agents are in common clinical use and are currently being provided by school-based oral health programs in NYC schools, have multiple randomized human clinical trials and systematic reviews indicating their efficacy in controlling caries, have American Dental Association billing codes, and are reimbursed by Medicaid and private insurers.

Manufacturer's information on each is provided below.

Fluoride Varnish

Proprietary Name: PreviDent® Varnish Mint, Grape and Raspberry
510(K) Number: K132109
Classification Name: Varnish, Cavity
Device Class: 2
Manufacturer: Colgate Oral Pharmaceuticals, [name]
Indications for Use: PreviDent[®] Fluoride Varnish is a topical fluoride for the treatment of dentinal sensitivity.

Composition: PreviDent[®] 5% Sodium Fluoride Varnish contains 22,600 ppm fluoride. It has a strong desensitizing action when applied to dental surfaces, treating hypersensitivity quickly and easily. This product sets rapidly on contact with saliva, resulting in patient comfort and acceptance. PreviDent[®] Varnish will leave a thin film on the teeth after application.

Treatment Regimen:

- 1. Wash and dry tooth surface
- 2. Mix well prior to application
- 3. Apply product with supplied brush in the conventional manner
- 4. Apply a thin amount of varnish on the tooth's surface until the varnish surface is dry
- 5. Dispose of package and applicator after use

Post Application Instructions:

- 1. Hardens on contact with saliva so the patient may leave immediately after application of the product
- 2. It is recommended that the patient be instructed to eat only soft foods for 2 hours after treatment

Fluoride Varnish

Proprietary Name: FluoroDose®

510(K) Number: K982915

Classification Name: Varnish, Cavity

Device Class: 2

Manufacturer: Centrix, Inc., [name]

Indications for Use: FlouroDose® Fluoride Varnish is a topical fluoride for the treatment of dentinal sensitivity

Composition: FluoroDose® contains 5% Sodium Fluoride (NaF) or 22,600 ppm fluoride. FluoroDose is lactose, gluten free and **nut free**

Treatment Regimen:

- 1. Clean teeth and remove excess moisture from area to be treated
- 2. Grip the foil cover and slowly peel back, exposing the brush applicator and varnish well
- 3. Remove applicator brush and stir material in well
- 4. Paint a thin film of varnish onto treatment area
- 5. Let the varnish dry for approximately 10 seconds and then instruct the patient to close their mouth
- 6. Dispose of package and applicator after use

Post Application Instructions:

- 1. Patients may leave immediately after treatment
- 2. Patient should be advised to remain on a soft food diet and only drink cold liquids for two hours after treatment
- 3. Patients should be instructed not to brush for a minimum of 4 to 6 hrs.

Silver Diamine Fluoride

Proprietary Name: Diamine Silver Fluoride Dental Hypersensitivity Varnish

510(K) Number: K102973

Classification Name: Silver Dental Arrest

Device Class: 2

Manufacturer: Elevate Oral Care, [name]

Indications for Use: Silver diamine fluoride is a clear liquid. It is applied to sensitive teeth, carious lesions, and pits and fissures using Advantage Arrest Applicators. The concentration of fluoride in SDF and fluoride varnish are indicated in the table below:

Fluoride product	Unit dose (ml)	Concentration (ppm)	F ion mg/ml	Fion mg/dose	
SDF 38%	1 drop (0.05)	44,800	44.8	2.24	
FV	0.25	22,600	22.6	5.65	
5% NaF	0.4	22,600	22.6	9.04	
	0.5	22,600	22.6	11.3	

Composition:

Desensitizing Ingredient: Aqueous Silver Diamine Fluoride, 38.3% to 43.2% w/v Inactive Ingredients: Purified water, FD&C Blue 1

Treatment Regimen:

- 1. Isolate the affected area of the tooth with cotton rolls
- 2. Clean and dry the affected tooth surface
- 3. Dispense 1-2 drops of solution into a dappen dish
- 4. Transfer material directly to the tooth surface with an advantage arrest applicator brush for approximately 30 seconds

5. Allow to dry, do not rinse

Post Application Instructions:

1. If accidental contact with skin or clothing occurs gently apply immediately with soap and water

5.2 Method for Assigning Subjects to Treatment Groups

This is a cluster randomized controlled design. A computer generated randomization sequence will assign schools to simple or complex treatment.

5.3 Implantation of Study Device

Silver diamine fluoride, along with all fluoride varnish materials are stored in a locked closet at NYU Dentistry. As indicated in 5.1, after drying the affected tooth surface, silver diamine fluoride is applied with an Advantage Arrest Applicators for approximately 30 seconds. The appropriate fluoride varnish is then applied to all teeth.

5.4 Subject Compliance Monitoring

N/A

5.5 Prior and Concomitant Therapy

Prior therapy is noted on the clinical examination. The only concomitant therapy provided in this study is fluoride varnish. All children are referred to a local dentist or community health center for follow on care. However, our experience is that only approximately 10% of parents follow through. Therefore, we see children once or twice per year. Using complex prevention, we achieve ~50% reduction in untreated caries, and almost complete elimination of toothaches.

5.6 Packaging

Silver diamine fluoride is available in an 8 oz. plastic bottle. One to 2 drops of liquid are dispensed into a dappen dish for delivery to the affected area using Advantage Arrest Applicators.

5.7 Blinding of Study

Neither the participants or clinicians are blinded. The analysts, however, are blinded.

5.8 Receiving, Storage, Dispensing and Return

5.8.1 Receipt of Study Device

Upon receipt of the of the silver diamine fluoride, an inventory will be performed and a device receipt log filled out and signed by the person accepting the shipment. The designated study staff will count and verify that the shipment contains all the items noted in the shipment inventory. Any damaged or unusable study devices in a given shipment will be documented in the study files. The investigator will notify the study sponsor of any damaged or unusable study devices that were supplied to the investigator's site.

5.8.2 Storage

Silver diamine fluoride will be stored with other dental supplies in a locked closet on the 8th floor at NY. Do not freeze.

5.8.3 Dispensing

A drop of silver diamine fluoride is dispensed from the 8 ml plastic bottle into a dappen dish prior to application for each patient. Advantage Arrest Applicators are used to apply the solution to pits, fissures, and frank caries for 30 seconds. Following application of the silver diamine fluoride varnish is applied.

5.8.4 Return

Typically, we completely use all of an 8 ml plastic bottle each day, as a bottle provides enough liquid to care for approximately 150 children. We dispose of the empty or partially empty bottle each day.

6 Study Procedures

6.1 Description

6.1.1 Informed Consent

All students enrolled in the 76 participating elementary schools, with paper or electronic informed consent signed by the parent/guardian, will receive caries prevention currently recommended by systematic reviews and national guidelines. Care will be provided independently of a family's ability to pay. Informed consent will be active for the entire time the child is in the school. Each year any newly enrolled students at the school will have the opportunity to join the program and be enrolled in the study if the parent/guardian signs the paper or electronic informed consent. If guardianship of the child changes during this time a new paper or electronic informed consent will need to be signed. The consent form is valid for 5 years or as long as the child is in NYC schools.

To facilitate accurate informed consent and student tracking we will request student rosters from the NY City Department of Education (NYC DOE). This will facilitate tracking students longitudinally. All forms will be translated into the major languages of NYC school children's parents. Those languages are Arabic, Bengali Bangla, Chinese, English, French, Haitian Creole, Korean, Russian, Spanish and, Urdu.

Blank IRB-approved paper informed consent will be distributed during Caried*Away* community engagement events and or mailed to students at the beginning of each school year in concert with all other school notifications. Parents can also choose to sign their child up for the program at their child's school. The current IRB approved blank informed consent will include a prepopulated personalized principal recruitment letter from the principal, the parent/guardian alternate location recruitment letter, the parent/guardian recruitment flyer, program information, a health history, the NYU Langone Health COVID-19 research participant information sheet and, the blank informed consent to be filled out for signature by the parent/guardian.

Completed parent/guardian signed and dated paper informed consent will be returned to the school and collected by the research team. This protocol aligns with other school vision, hearing, and vaccination programs. Care will be provided to all children with informed consent. The information listed on the signed paper informed consent is loaded directly into the Apple password protected iPad to create the child's secure electronic dental record.

Electronic informed consent forms will be distributed in addition to the established protocol for the distribution of paper consent forms to participating sites (schools). The following protocol will be followed for eICF distribution:

Electronic informed consent can be distributed by a clinical team member using the Caried*Away* new enrollee email written in English or Spanish using the following hyperlinks:

- English language eICF: https://is.gd/CariedAwayNYC
- Spanish language eICF: https://is.gd/CariedAwayNYC_SP

Electronic informed consent can be distributed by the schools in English or Spanish using whichever existing method the school uses for mobile phone contact, in emails, or on the school's social media page in the following ways:

NYU Caried*Away* Website URL by selecting "registering your child"
 English

- https://dental.nyu.edu/faculty/epidemiology-health-promotion/pcori-grant.html
- Short URL: https://is.gd/CariedAwayNYC
- 2. Spanish
 - https://dental.nyu.edu/faculty/epidemiology-health-promotion/pcori-beca.html
- 2) Hyperlinks in English and Spanish
 - English language eICF: https://is.gd/CariedAwayNYC
 - Spanish language eICF: https://is.gd/CariedAwayNYC SP

The parent or legal guardian fills out the eICF and uses 'scratch' method (mouse, stylus, or finger) to sign and then returns the completed ICF via Redcap.

Only select study investigators will have access to the eICF data, which will be stored on REDCap. This includes the principal investigators, the clinical research coordinator, the study administrator, the clinical director, the IRB coordinator and NESS.

The study administrator will then cross-reference the OSIS number in the original .csv file which was provided to us at the beginning of each school year by the NYC Department of Education, and verify that the correct OSIS number was provided correctly by the consenter.

The study administrator then uploads all of the informed consent PDF's to NESS via the secure and password protected ShareFile link listed below:

• https://nedental.sharefile.com

NESS then uploads each student's eICF to their electronic dental record in the iPad.

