3.2 Primary Study Endpoints

Caries arrest and prevention will be determined at each visit. The primary end point for caries arrest will be at 2 years, and follow on to termination of trial determine the length of time that caries remains arrested. The primary end point for caries prevention will be at 3 years, and follow on to termination of trial to determine stability of prevention.

Presence / absence of caries is assessed by visual/tactile methods. Sound tooth surfaces appear white and smooth. Active caries appear brown and soft. Arrested caries appear dark brown or black and hard.

For clinical assessment, we will train and standardize clinicians using validated criteria implemented by the Centers for Disease Control and Prevention (CDC) in the National Health and Nutrition Examination Surveys (NHANES). Training and validation were developed and documented by our Colleague, [name], while at the CDC and field tested in the examination of special athletes^{23,24}. Training and standardization of these examiners implement the World Health Organization guidelines^{25,26}.

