6.5.2 Blinding

As a pragmatic trial, this is non-blinded for the participants. Neither schools, nor teachers, nor students, nor clinicians will be blinded. Clinicians will work in teams that only provide either simple or complex prevention. The analysts will be blinded as to the care provided to students in a particular school.

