7.1 Sample Size Determination

The study is powered to the primary outcomes of caries arrest and caries prevention between twice-yearly simple and complex prevention. We expect to enroll approximately 14,100 students across the initial 60 schools over the duration of the study (N=235 per cluster). The remaining 16 schools will contribute approximately 3760 participants. From our pilot studies of school-based caries prevention, baseline caries prevalence is approximately 40%. Our power estimates assume an equal proportion of success, π , of 20% caries arrest. With a given non-inferiority margin (δ) of 10%, a total sample size per group of 198 (N_{tot} = 396) is required for an alpha of 5% and a power of 80%²⁹. However, as we use a cluster randomized design, this sample size is inflated to account for clustering (intraclass correlation coefficient = .10) by a design effect of 24.4 to a total required sample of 9,662.

For caries prevention, both interim therapeutic restorations and silver diamine fluoride have been shown to be 80% efficacious in individual clinical trials. Power for the repeated measures design was estimated using the method of Diggle et al (2002) for generalized estimating equations ³⁰. For power estimates, we control for the baseline prevalence of untreated decay. We assume a conservative average number of visits per child of 6, with a power of .80 and an alpha of 5%. We further assume a repeated measures correlation of 0.5 and a per-visit attrition rate of 20%. For a given minimally detectable effect size (standardized effect size difference) of .25, an attrition and clustering adjusted sample size of 12,874 is required. Thus, our study is powered for these conservative assumptions for caries prevention. Further, we note that in the presence of the nonlinear link function, ME-GLM is more powerful than GEE, thus our power estimates are conservative and the anticipated sample size is sufficient for analysis.

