8.23 Schedule and Content of Reports

Enrollment reports will be reviewed biannually, as study enrollment will be conducted in the fall semester of each school year. Review will thus occur in the spring of the same academic year. Enrollment reports and other study reports will be presented to study stakeholder groups on a quarterly basis, as will reports of study conduct. All data will be masked to study investigators as

data are de-identified at the BEDAC prior to being sent to investigators for analysis. The study PIs and biostatisticians do not have access to the identification code key. Finally, participating schools and students will be assigned IDs prior to data collection.

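### Children consent after their school's arm is known and can join every year, yet baseline untreated decay, controlled for in the power section, is not named in either primary model

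*Combined protocol and SAP*

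**What the plan says.** Section 4.2.2 randomises 30 schools in Year 1 and 30 more in Year 2, with consenting children followed for five and four years respectively. Child-level entry stays open after that. Section 6.1.1: "Each year any newly enrolled students at the school will have the opportunity to join the program and be enrolled in the study". Section 8.23 adds that "study enrollment will be conducted in the fall semester of each school year".

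The arm is not hidden from those who recruit or join. Section 6.5.2: "Neither schools, nor teachers, nor students, nor clinicians will be blinded", and "Clinicians will work in teams that only provide either simple or complex prevention". Section 4.2.1 gives clinical staff a part in recruitment: "After a clinical team member speaks with the parent/guardian of a new participant, the clinical team member will send the parent/guardian the" study's e-mail for new enrollees, with the consent link. Only the analysts are blinded.

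On baseline decay, the sections differ. Section 7.1, on prevention: "For power estimates, we control for the baseline prevalence of untreated decay". Section 6.4 lists the a priori confounders as gender, previous or concurrent dental treatment, age, race/ethnicity and school-level indicators. Section 7.2 specifies a multilevel binomial model for arrest and GEE for prevention, and neither names baseline decay. Section 7.3 analyses all participants as randomised, with no term or set for time of entry.

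On timing, section 3.2 puts the arrest endpoint at 2 years and states: "The primary end point for caries prevention will be at 3 years". Section 7.1: "We expect to enroll approximately 14,100 students across the initial 60 schools over the duration of the study".

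**The concern.** Randomising schools balances the schools, in expectation. It does not balance the children who later choose to take part when the school, the staff and possibly the family know which treatment is on offer. If that knowledge affects who joins, the arms can differ in baseline caries risk, and the standard error does not reflect this. In a non-inferiority comparison the harmful direction is a bias favouring simple prevention, because it can produce a false claim.

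Untreated decay at first examination is the obvious variable to protect the comparison. Section 6.1.6 already records it for every tooth. The previous-treatment covariate in 6.4 describes treated teeth, so it does not replace it.

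Time of entry raises a second, narrower issue, mainly for arrest. Section 7.2 scores a child by the share of treated lesions that remain arrested until the study ends. That is easier to meet after one year of observation than after four, and the plan has no analysis that separates short from long follow-up.

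**Working it through.** **1. The plan's own figure.** Inputs from 7.1: success proportion 0.20 in both arms, margin 0.10, alpha 5%, power 80%, ICC 0.10, 235 children per school.

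- n per group = (1.645 + 0.842)² × 2 × 0.20 × 0.80 / 0.10² = 197.8, so 198. This matches the plan and shows that its 5% is one-sided (one-sided 2.5% would give 252).
- Design effect = 1 + (235 − 1) × 0.10 = 24.4.
- 396 × 24.4 = 9,662, as stated.

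I could not tie the prevention requirement of 12,874 to one formula, and nothing below rests on it.

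**2. What an imbalance would do.** Bias in the outcome contrast = (arm difference in the share of children with baseline decay) × (difference in outcome risk between children with and without decay). Both factors are assumptions. The documents give only the overall baseline prevalence of about 40%.

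- 0.05 × 0.20 = 0.010, which is 10% of the margin.
- 0.05 × 0.40 = 0.020, which is 20% of the margin.

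Standard error with 30 schools per arm and m = 235: √(2 × 0.16 × 24.4 / (30 × 235)) = 0.0333.

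If the bias favours simple prevention, the one-sided 5% error becomes 1 − Φ(1.645 − bias/0.0333):

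- bias 0.010: 8.9%
- bias 0.020: 14.8%

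If it runs against simple prevention, power when the arms are truly equal, Φ((0.10 − bias)/0.0333 − 1.645), falls from 91.3% to 85.5% and 77.6%.

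This borrows the arrest margin and proportion, because 7.1 sizes prevention on a standardised effect of 0.25 instead. In the arrest model every child has decay, so the same arithmetic applies to an imbalance in the share of children with a high lesion count. With the smaller arrest set in step 4 (standard error 0.0342), the errors are 8.8% and 14.5%.

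**3. Who can reach the endpoints.** The documents give no entry-year distribution. Assume that 40% to 80% of a school's participants join in its first year and the rest join evenly over its remaining years (four for the first wave, three for the second), with the two waves weighted equally. Counting whole school years, a Year 5 joiner cannot reach 2 years, and a Year 4 or Year 5 joiner cannot reach 3 years.

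- Cannot reach 2 years: between (0.05 + 0.067)/2 = 6% and (0.15 + 0.20)/2 = 18%.
- Cannot reach 3 years: twice that, 12% to 35%.

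If the first examination is in fall and the last in spring of Year 5, each limit moves one year earlier, giving 12% to 35% and 18% to 53%.

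**4. Power cost of an entry-time sensitivity set.** Only children with lesions inform arrest: 0.40 × 235 = 94 per school. Power = Φ(0.10/SE − 1.645), with SE = √(2 × 0.16 × (1 + (m − 1) × 0.10)/(30m)).

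- m = 94: design effect 10.3, SE 0.0342, power 90.0%.
- m = 47 (half, assumed): design effect 5.6, SE 0.0356, power 87.7%.

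The loss is small because at an ICC of 0.10 the precision comes mainly from the number of schools.

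**The case against.** The case on the other side has four parts.

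**The covariate list is open.** Section 6.4 introduces its list as examples, and 7.1 shows that the investigators had baseline decay in mind. A reader might infer that the plan decided against adjustment. The text does not support that; it is a mismatch between sections. It still needs correcting, because a covariate that no model names is not pre-specified.

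**Selective joining is not demonstrated.** The consent pages are not among the documents available here, so what parents are told about the assigned arm is unknown. Section 6.6 also monitors consent rates and caries prevalence, at school, grade and clinician level. This stands: there is a route for bias but no evidence that it operates. That monitoring is not by arm.

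**Late joiners are not wasted for prevention.** The GEE in 7.2 works by follow-up interval, so a child who enters late contributes valid intervals without reaching 3 years. A reader might infer that the 14,100 overstates the usable sample and leaves the trial short of power. The documents do not support that: 7.1 labels the figure as enrolment over the whole study, and step 4 shows little loss for arrest.

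**Restriction is not the answer.** A reader might want the primary set cut to children seen in each school's first care year. That would drop first-wave children who join later but can still reach the endpoints, and it would conflict with 7.3. It would also leave much of the problem in place, since first-year children consent after randomisation too.

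**Conclusion.** The concern holds as a gap in pre-specification. Entry is open, unblinded and after randomisation, and the baseline variable best placed to protect the comparison appears in the power section but in neither primary model. The exposure covers first-year as well as later entrants.

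Its size and direction cannot be found from the documents. Under the stated assumptions (5-point imbalance, 20 to 40 point risk difference) the shift is 1 to 2 points, and a one-sided 5% error becomes about 9% to 15% if the shift favours simple prevention. A reader might set the 5-point imbalance directly against the 10-point margin and call it half. That is not valid: the margin is on the outcome, and an imbalance reaches the outcome only after multiplication by the risk difference.

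Entry time matters most for arrest, because of how that outcome is defined. The issue there is bias and an unclear follow-up window; loss of power is minor.

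**What to change.** 1. In 6.4 and 7.2, name each child's untreated decay at first examination as a covariate in both primary models. For the prevention GEE, use baseline status and count. For the arrest model, use baseline lesion count, because presence or absence does not vary among children who all have decay.
2. Keep the primary population in 7.3. Add a sensitivity analysis limited to children who entered early enough to reach 2 years (arrest) or 3 years (prevention), with the entry cut-off stated in advance for each wave.
3. Report consent rate and baseline decay by arm and entry year. Do this with the final analysis, since 8.14 keeps the study report tables aggregated across groups.

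The cost is SAP wording and slightly more analysis work; the baseline examination and the dates of entry are already collected. The sensitivity set has somewhat less power (87.7% against 90.0% for arrest if half the children remain). Adjustment deals only with measured baseline decay. Other differences between those who join in each arm would remain, which is why the by-arm table is needed as well.
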